12.2.2. Control of Systematic Error/Bias

Selection of patients will be made from the Investigator's usual patient load. All patients meeting the inclusion/exclusion criteria and having signed the Informed Consent Form will be eligible for participation in the study. The reasons for exclusion, for subjects who sign an informed consent form but are not implanted, will be indicated in EDC. Boston Scientific will report to the ethic committee any evidence of fraud, including deliberate tampering with the selection of subjects.

[Redacted]

[Redacted]

12.3. Data Analyses

All statistical analyses will be done using the SAS System software, version 8.2 or later (Copyright © 2000 SAS Institute Inc., SAS Campus Drive, Cary, North Carolina 27513, USA. All rights reserved).

[Redacted]

[Redacted]

[Redacted]

[Redacted]

[Redacted]

[Redacted]

[Redacted]

[Redacted]

[Redacted]

[Redacted]

[Redacted]

be issued to the site for appropriate response. Site staff will be responsible for resolving all queries in the database.

13.1.1. Electronic Questionnaires

Questionnaires in electronic form may be collected directly using an electronic data collection platform at the clinical site (e.g. iPad). After completion by the subject or a clinician, data from the electronic questionnaires are transmitted directly into the EDC system.

13.1.2. Direct Data Upload

For quality assurance purposes and validation, technical data on the SCS device will be collected using direct data upload to a secure BSC server. BSC Field personnel, who assist in programming the device settings per routine care, will upload the device files to a secure server stored in a restricted location at BSC.

Device files will also be uploaded into the EDC system.

13.2. Study Assessments

13.2.1. Adverse Events

Adverse event evaluation will be conducted to identify adverse events occurring during the study and classify them in regards to seriousness, relationship to the implant procedure and/or device, action taken and outcome. Safety events will be reported as specified in Table 20.4-1.

All device and procedure related non-serious adverse events, all serious adverse events, and unanticipated adverse events will be collected from the time of consent through the end of the study.

13.2.2. Beck Depression Inventory (BDI-II)

BDI-II measures the intensity, severity, and depth of depression. It includes a long form of 21 questions, each evaluating a specific depression symptom (e.g., sadness, pessimism, irritability, loss of energy, concentration difficulty, indecisiveness, changes in sleep pattern, fatigue, etc.).

13.2.3. Concomitant Medications

All opioid pain-related medications will be collected throughout the study in order to obtain a full record of medication-related resource utilization. Information will include medication name, dates of prescription, indication or purpose, dose, frequency, and route of administration.

13.2.4. Clinical Global Impression of Change (CGI-C)

CGI-C is a seven-point scale that requires the clinician to assess how much the subject's condition has improved or worsened relative to the subject's enrollment in the study. The clinician will rate the subject's change as: very much improved; much improved; minimally improved; no change; minimally worse; much worse; or very much worse.

13.2.5. Demography

Demographic information will include date of birth, gender, and race/ethnicity.

13.2.6. EQ-5D 5 Level (EQ-5D-5L)

EQ-5D-5L is a standardized measure of health status developed by the EuroQol Group in order to provide a simple, generic measure of health for clinical and economic appraisal. Applicable to a wide range of health conditions and treatments, it provides a simple descriptive profile and a single index value for health status that can be used in the clinical and economic evaluation of health care as well as in population health surveys.

EQ-5D-5L is comprised of a descriptive system and a visual analog scale. The descriptive system measures quality of life along five dimensions, including mobility, self-care, usual activities, pain/discomfort, and anxiety/depression, with five levels for each dimension from which subjects are asked to select one. The visual analog scale is used to record the subject's self-rated health on a 20cm vertical line with endpoints labeled 'the best health you can imagine' and 'the worst health you can imagine'.

13.2.7. Medical History

Medical history will include medical and procedural history relating to pain management, onset of chronic pain, all pain-related diagnoses and medical/psychological conditions, medication use etc.

13.2.8. Oswestry Disability Index Version 2.1a (ODI v2.1a)

ODI v2.1a assesses the degree of subject disability due to pain, measuring the impact of pain on activities of daily living. ODI v2.1a is composed of 10 questions that describe the pain and its impact on daily life on a 0 - 5 scale, with higher values indicating the more severe impact.

13.2.9. Pain Intensity: NRS

Pain Intensity: NRS is a questionnaire that assesses the intensity of the subject's pain intensities, including overall, leg, and low back pain over the past 7 days. Pain intensity is expressed on a 0 – 10 numerical rating scale (NRS), where 0 indicates "no pain" and 10 indicates "pain as bad as you can imagine" as self-reported by the subject.

13.2.10. Pain Intensity: VRS

Pain Intensity: VRS is a questionnaire that verbally assesses the intensity of the subject’s pain intensities, including overall, leg, and low back pain over the past 7 days. This is done based on a clinician interview (e.g. study personnel such as physician or study coordinator) with the subject.

Pain intensity is expressed on a 0 – 10 verbal rating scale (VRS), where 0 indicates “no pain” and 10 indicates “pain as bad as you can imagine”, verbally reported by the subject to study personnel.

13.2.11. Procedure Information

General information will be collected regarding the SCS procedures performed during the study, including implant, explant and revision procedures.

13.2.12. Patient Global Impression of Change (PGI-C)

PGI-C is a seven-point scale that requires the subject to assess how much their condition has improved or worsened relative to their baseline. Subjects will rate themselves as: very much improved; much improved; minimally improved; no change; minimally worse; much worse; or very much worse.

13.2.13. Percent Pain Relief (PPR)

PPR is a questionnaire assessing how much of the subject’s low back pain and leg pain has been relieved by the SCS treatment. Pain relief is expressed as a percentage from 0 – 100%.

13.2.14. Preference Questionnaire

The Preference Questionnaire assesses the subjects’ preference for treatment based on the options offered during the study.

13.2.15. Programming Parameters

Standard information regarding the programming parameters used to program the subject’s IPG, as well as measurements taken using the device (e.g. contact impedances) will be collected from the Clinician Programmer (CP).

13.2.16. Resource Utilization Inventory (RUI)

Health-related resource utilization data will be collected to support the health economic analyses. Resource utilization categories include: office/hospital visits, diagnostic tests, and non-surgical procedures.

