6.1. Primary Objective

The primary objective of this study is to demonstrate the value of multiple modalities and sustained clinically significant pain relief in patients with chronic pain when using the Boston Scientific Spectra WaveWriter Spinal Cord Stimulator (SCS) System.

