7.1. Primary Endpoint

The primary endpoint is the proportion of subjects with 50% or greater reduction from the Baseline Visit in average overall pain intensity at 3 months post activation, with no increase in baseline average daily opioid medications used to treat pain.

[REDACTED]

[REDACTED]

[REDACTED]

[REDACTED]

[Redacted text block]

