11.16.2. Interventional Pain Procedures

No interventional pain procedures to treat the SCS-targeted pain are allowed through the 3-Month Visit. Procedures associated with the SCS device (e.g. IPG Revision, Lead revision, CSF leak interventions and interventions associated with SCS procedure related adverse event management) are allowed. Excluded procedures include, but are not limited to, the following:

- Epidural steroid injection
- Facet joint injection
- Selective nerve root block
- Radiofrequency ablation
- Spine surgery (e.g., discectomy, vetebroplasty, fusion)

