11.17. Medication Requirements

Opioid Medication Lock Period (Medication Lock visit to 3-Month Visit):

Investigators/Subjects will not be allowed to change opioid pain medications from the Medication Lock visit until completion of the 3-Month Visit. Type/dose/route must remain unchanged.

The use of acute opioid pain medication for procedural discomfort is allowed during the Procedures and Healing Period and in the event of the revision or replacement of leads, extensions and/or IPG, per site’s routine care.

Opioid Medication Open Period (3-Month Visit to End of Study visit)

Investigators/Subjects may change opioid pain medications during the pain medication open period, from the 3-Month Visit to the 1-Year, End of Study Visit as needed.

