Underlying diseases are not reported as AEs unless there is an increase in severity or frequency during the course of the investigation. Death should not be recorded as an AE, but should only be reflected as an outcome of a specific SAE.

Any AE experienced by the study subject after informed consent, whether during or subsequent to the procedure, must be recorded in the eCRF.

Refer to Section 19 for the known risks associated with the study device(s).

NOTES:

1. For the purposes of this study, hospitalization is defined as any in-patient admission.
2. Hospitalizations occurring for the purpose of performing a planned procedure as per routine care such as implant procedures, or follow-up visits, are not to be reported as a SAE. However, complications or adverse events that occur during the planned procedure should be reported as (S)AEs if they meet the protocol specified definitions.
3. Elective/planned hospitalization(s) need not be reported as an SAE. However, complications or adverse events that occur during an elective/planned hospitalization, should be reported as (S)AEs if they meet the protocol specified definitions.
4. In the event of subject death during the conduct of the study, efforts should be made to perform an autopsy.
5. Sensations or side effects that occur during the programming session should not be reported as AEs. However, undesired sensations or side effects caused by the final programming parameters (including active contact, pulse width, frequency, and amplitude) that persist or occur after the completion of the programming should be reported as AEs.
6. Lack of efficacy/decreased therapeutic response should not be reported as AEs. Clinical sequelae, other than pain, that occur as a result of lack of efficacy/decreased therapeutic response should be reported as AEs
7. Clinically significant worsening of the pattern of intensity or distribution of Baseline pain symptoms should be reported as an AE.
8. Device deficiencies, including, but not limited to device/lead migrations, which are not associated with an adverse clinical outcome should only be reported as device deficiencies. However, if a device deficiency precipitates an AE, the AE should be reported in the *Adverse Event* eCRF and the device deficiency should be documented in the *Device Deficiency* eCRF.

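### After the 3-Month Visit no visible form has a category for spine surgery for the treated pain, which weakens attribution of 6- to 12-month relief to the device

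*Combined protocol and SAP*

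**What the plan says.** - **Objective (Section 6.1).** The study is to "demonstrate the value of multiple modalities and sustained clinically significant pain relief in patients with chronic pain".
- **Primary endpoint (Section 7.1).** It is a responder rate on "average overall pain intensity at 3 months post activation, with no increase in baseline average daily opioid medications used to treat pain".
- **Later pain scores (Table 11.1-1).** NRS and VRS pain are repeated at 6, 9 and 12 months.
- **Procedures (Section 11.16.2).** "No interventional pain procedures to treat the SCS-targeted pain are allowed through the 3-Month Visit". The list of excluded procedures includes spine surgery. No visible text sets a rule for the period afterwards.
- **Opioids (Section 11.17).** From the 3-Month Visit to Year 1, "Investigators/Subjects may change opioid pain medications during the pain medication open period". Section 13.2.3 has all opioid pain medication recorded throughout, with dates, indication, dose, frequency and route.
- **Resource Utilization Inventory (RUI; Section 13.2.16; baseline, 3, 6, 9 and 12 months).** "Resource utilization categories include: office/hospital visits, diagnostic tests, and non-surgical procedures".
- **Procedure Information (Section 13.2.11).** "General information will be collected regarding the SCS procedures performed during the study, including implant, explant and revision procedures".
- **Safety (Section 20.2, Notes 3, 6 and 7).** "Elective/planned hospitalization(s) need not be reported as an SAE". Loss of efficacy is not to be reported as an adverse event, but clinically significant worsening of baseline pain is.

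**The concern.** For the 3-month result the sponsor guards against competing treatment in two ways: the responder definition disallows an opioid increase, and procedures for the treated pain are barred. From Month 3 to Month 12, which is 9 of the 12 months of follow-up, neither restriction on care applies. The later scores are the visible pain-intensity data that bear on whether relief lasted.

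Subjects whose stimulation is fading are the ones most likely to seek other treatment. If one of them has spine surgery for the same pain and then reports at least 50% relief at Year 1, the score reads as a response to stimulation. The bias would probably favour the device. An analyst can deal with this if the treatment is in the database, so the question is which of the competing treatments are captured.

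**Working it through.** There is no figure in the plan to reproduce. The check sets each competing treatment against the forms that could hold it, and then bounds the effect.

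**Step 1. Capture after Month 3**

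| Treatment | Status after the 3-Month Visit | Where recorded |
|---|---|---|
| Opioid change | Expressly allowed (11.17) | Concomitant Medications, with dates, dose and indication (13.2.3); scheduled through Year 1 and at unscheduled visits (Table 11.1-1) |
| Injection, block, ablation | No longer barred, by implication (11.16.2) | RUI non-surgical category at 6, 9 and 12 months (13.2.16) |
| Spine surgery for the treated pain | No longer barred, by implication (11.16.2) | No named category on any visible form |

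Opioid increases can be identified in analysis. Non-surgical procedures have a place, although Section 13.2.16 describes the RUI as serving health-economic analyses and does not say whether date and indication are kept. Surgery is the clear gap.

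**Step 2. Indirect traces of surgery**

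- *RUI hospital visit.* It may count the stay. Nothing says that it names the operation or the reason.
- *Adverse event for worsened pain (20.2, Note 7).* The form holds the treatment given (Table 20.4-1). But a subject whose relief fades and whose pain returns to its baseline level fits Note 6, which keeps loss of efficacy off the adverse event form. That is the case that matters most here.
- *SAE.* An unplanned admission would be reported; Note 3 exempts a planned one.
- *Discontinuation (10.2).* Surgery affecting the IPG or leads is a listed ground, but discontinuation is optional and surgery that spares the device is not covered.
- *Procedure Information at unscheduled visits (Table 11.1-1).* Its content is limited to SCS procedures by Section 13.2.11.
- *Medical History.* Scheduled at baseline only.
- *Site charts (11.19).* They hold procedures but stay at the site.

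Each may leave a hint. None reliably yields a dated, indication-specific record.

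**Step 3. Bound on the effect**

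Let p be the observed late responder proportion, s the share of subjects with unrecorded surgery for the treated pain, and f the fraction of those who respond only because of it. The proportion not owed to surgery is p − f·s, and the worst case is f = 1. Neither p, s nor f is in the documents; all are assumed.

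With p = 60% and f = 1:

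| s | p − s |
|---|---|
| 1% | 59% |
| 2% | 58% |
| 5% | 55% |
| 10% | 50% |
| 20% | 40% |

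Taking the plan's 3-month performance criterion of 40% purely as a reference level, the share needed to bring p down to it is p − 40%: 10 points at p = 50%, 20 at p = 60% and 30 at p = 70%. The late results lose at most s points, and would become uninformative only if such surgery were common.

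**The case against.** The case on the other side is substantial.

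- **Most competing treatment is recorded.** This stands. Opioids are captured in full and non-surgical procedures have a category, so the capture gap is confined to surgery.
- **The RUI list need not be exhaustive, and surgery leaves traces.** This stands in part. It is why the point is that no visible form has a category for such surgery, not that surgery could never appear. Step 2 shows why the traces are not a dependable substitute.
- **Surgery near the system might lead to discontinuation**, leaving no Year 1 score to inflate. This is possible but not assured.
- **The rules for later visits are redacted.** This stands. A rule for late opioid increases or procedures may exist and cannot be called missing. Even so, a rule cannot adjust for an operation that was never captured.
- **Outcome regardless of later care is a legitimate estimand** for a commercially approved device. This stands, and it is why the composite below is proposed only as a supportive analysis.

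A reader might infer that the 6- to 12-month scores cannot show sustained relief at all. The documents do not support that. The scores can show whether relief lasted; what is weakened is attribution to the device, which the single-arm, open-label design already limits.

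A reader might also put the inflation at 5 to 10 points, by assuming that 10% to 20% of subjects take up other treatment and half then respond (10% × 0.5 = 5; 20% × 0.5 = 10). Those inputs are not in the documents, they pool recorded opioid increases and non-surgical procedures with surgery, and they suppose that none of these subjects would have responded otherwise.

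**Conclusion.** The point holds as a gap in data capture. After the 3-Month Visit, spine surgery for the treated pain is no longer barred, yet no visible form has a category for it, and the indirect traces do not reliably identify it. Attribution of 6- to 12-month relief to the device is weakened, probably in the device's favour. That direction rests on the assumption that subjects with failing stimulation are the likeliest to have surgery.

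The size is unknown. The overstatement is at most the share of subjects operated on for that pain, and it may be small if such surgery is rare. The 3-month primary endpoint lies inside the restricted period and is unaffected. The conclusion rests on the unredacted text and makes no claim about what the redacted endpoint and analysis sections contain.

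**What to change.** Leave patient care as it is and change what is recorded and reported.

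1. In Table 11.1-1 and Section 13.2.11, extend Procedure Information to any interventional or surgical procedure for the SCS-targeted pain, with type, date and indication, asked at the 6-, 9- and 12-month visits and at unscheduled visits. Asking about non-surgical procedures here too supplies the date and indication that the RUI is not described as holding.
2. Unless the redacted text already does so, add a supportive analysis beside the unrestricted 6-, 9- and 12-month responder rates. It would count as non-responders those subjects with such a procedure or with an opioid increase over baseline. The unrestricted rate stays in the report.

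The cost is one added item on an existing eCRF and a short definition in the analysis plan. The supportive late responder rate may come out somewhat lower than the unrestricted one. The capture item is the more urgent of the two, because surgery data not collected during follow-up are hard to recover after database lock.

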13.2.17. Short-Form Health Survey 36 Item (SF-36v2)

The SF-36v2 measures subjects’ functional health and well-being from their own point of view. SF-36v2 is comprised of 36 questions spanning eight health domains: physical functioning, role-physical, bodily pain, general health, vitality, social functioning, role-emotional, and mental health. All health domain scales contribute to the scoring of two component summary measures: physical health and mental health.

13.2.18. Therapy Rating

The Remote Control has a therapy rating feature. Subjects may be instructed to perform therapy ratings at a frequency that may be up to daily. Information regarding therapy ratings will be collected from the Clinical Programmer, as applicable.

13.2.19. Treatment Satisfaction Questionnaire for Medication – modified (TSQM-9m)

TSQM-9 is a 9-item instrument validated for the assessment of subjects’ satisfaction with a medication across three domains: effectiveness, convenience, and global satisfaction. TSQM-9m is a slightly modified version developed for this study in which the term ‘medication’ is substituted for ‘device’ to be applicable with a medical device treatment.

13.2.20. Work Productivity (WPAI-SHP v2.0)

WPAI:SHP v2.0 assesses the amount of absenteeism, presenteeism, and daily activity impairment attributable to a specific health problem. The specific health problem in this study is chronic pain. WPAI:SHP v2.0 consists of six questions addressing the subject’s employment status, true work status, productivity while working, and ability to carry out regular daily activities.

13.3. Data Retention

The Principal Investigator or his/her designee or Investigational site will maintain, at the investigative site, all essential study documents and source documentation that support the data collected on the study subjects in compliance with ICH/GCP guidelines. Documents must be retained for at least 2 years after the last approval of a marketing application or until at least 2 years have elapsed since the formal discontinuation of the clinical investigation of the product. These documents will be retained for a longer period of time by agreement with BSC or in compliance with other country/regional/local regulations.

The Principal Investigator or his/her designee will take measures to ensure that these essential documents are not accidentally damaged or destroyed. If for any reason the Principal Investigator or his/her designee withdraws responsibility for maintaining these essential documents, custody must be transferred to an individual who will assume responsibility and BSC must receive written notification of this custodial change. Sites are required to inform Boston Scientific in writing where paper or electronic files are maintained in case files are stored off site and are not readily available.

14. Amendments

If a protocol revision is necessary which affects the rights, safety or welfare of the subject or scientific integrity of the data, an amendment is required. Appropriate approvals (e.g., IRB) of the revised protocol must be obtained prior to implementation.

15. Deviations

An Investigator must not make any changes or deviate from this protocol, except to protect the life and physical well-being of a subject in an emergency. An investigator shall notify the sponsor and the reviewing IRB of any deviation from the investigational plan to protect the life or physical well-being of a subject in an emergency, and those deviations which affect the scientific integrity of the clinical investigation. Such notice shall be given as soon as possible, but no later than 5 working days after the emergency occurred, or per prevailing local requirements, if sooner than 5 working days.

All deviations from the investigational plan, with the reason for the deviation and the date of occurrence, must be documented and reported to the sponsor using the EDC system. Sites may also be required to report deviations to the IRB, per local guidelines and government regulations.

Deviations will be reviewed and evaluated on an ongoing basis and, as necessary, appropriate corrective and preventive actions (including site re-training, or site termination) will be put into place by the sponsor.

[Redacted]

16. Device/Equipment Accountability

Commercially approved Spectra WaveWriter SCS Systems are used in this study per the Directions for Use; no investigational devices are used.

17. Compliance

17.1. *Statement of Compliance*

This study will be conducted in accordance with 21 CFR 50 and 56, ISO 14155: Clinical Investigation of Medical Devices for Human Subjects – Good Clinical Practice, the relevant parts of the ICH Guidelines for Good Clinical Practices, ethical principles that have their origins in the Declaration of Helsinki, and pertinent individual country laws and regulations. The study shall not begin until the required approval/favorable opinion from the IRB and/or regulatory authority has been obtained, if appropriate. Any additional requirements imposed by the IRB or regulatory authority shall be followed, if appropriate.

17.2. *Investigator Responsibilities*

The Principal Investigator of an investigational site is responsible for ensuring that the study is conducted in accordance with the Clinical Study Agreement, the Clinical Investigational Plan/Protocol, ISO 14155, applicable Code of Federal Regulations, ethical principles that have their origins in the Declaration of Helsinki, any conditions of approval imposed by the reviewing IRB, and prevailing local and/or country laws and/or regulations, whichever affords the greater protection to the subject.

The Principal Investigator’s responsibilities include, but are not limited to, the following:

- Prior to beginning the study, sign the Clinical Study Agreement and comply with the Investigator responsibilities as described in such Agreement.
- Prior to beginning the study, sign the Investigational Plan/Protocol signature page documenting his/her agreement to conduct the study in accordance with the protocol.
- Provide his/her qualifications and experience to assume responsibility for the proper conduct of the study and that of key members of the site team through up-to-date curriculum vitae or other relevant documentation and disclose potential conflicts of interest, including financial, that may interfere with the conduct of the clinical study or interpretation of results.
- Make no changes in or deviate from this protocol, except to protect the life and physical well-being of a subject in an emergency; document and explain any deviation from the approved protocol that occurred during the course of the clinical study.
- Report protocol deviations to the sponsor, IRB and/or regulatory authorities, as required by the protocol, IRB guidelines, and/or national/regulatory regulations.
- Create and maintain source documents throughout the clinical study and ensure their availability with direct access during monitoring visits or audits; ensure that all clinical investigation-related records are retained per requirements.
- Ensure the accuracy, completeness, legibility, and timeliness of the data reported to the sponsor in the CRFs and in all required reports.

- Record, report, and assess (seriousness and relationship to the device/procedure) every adverse event as applicable per the protocol and observed device deficiency.
- Report to the sponsor, per the protocol requirements, all SAEs and device deficiencies that could have led to a SADE and potential/USADE or UADE.
- Report to the IRB and regulatory authorities any SAEs and device deficiencies that could have led to a SADE and potential/USADE or UADE, if required by the national regulations or this protocol or by the IRB, and supply BSC with any additional requested information related to the safety reporting of a particular event.
- Maintain device disposition records and ensure that the device components are used only by authorized/designated users and in accordance with this protocol and Directions for Use.
- Allow the sponsor to perform monitoring and auditing activities, and be accessible to the clinical research monitor or auditor and respond to questions during monitoring visits or audit(s).
- Allow and support regulatory authorities and the IRB when performing auditing activities.
- Ensure that informed consent is obtained in accordance with applicable laws, this protocol and local IRB requirements.
- Provide adequate medical care to a subject during and after a subject's participation in a clinical study in the case of adverse events, as described in the Informed Consent Form (ICF).
- Inform the subject of the nature and possible cause of any adverse events experienced.
- As applicable, provide the subject with necessary instructions on proper use, handling, storage, and return of the device.
- Inform the subject of any new significant findings occurring during the clinical study, including the need for additional medical care that may be required.
- Provide the subject with well-defined procedures for possible emergency situations related to the clinical study, and make the necessary arrangements for emergency treatment.
- Ensure that clinical medical records are clearly marked to indicate that the subject is enrolled in this clinical study.
- Ensure that, if appropriate, subjects enrolled in the clinical study are provided with some means of showing their participation in the clinical study, together with identification and compliance information for concomitant treatment measures (contact address and telephone numbers shall be provided).
- Inform, with the subject's approval or when required by national regulations, the subject's personal physician about the subject's participation in the clinical study.

- Make all reasonable efforts to ascertain the reason(s) for a subject's premature withdrawal from clinical study while fully respecting the subject's rights.
- Ensure that an adequate investigation site team and facilities exist and are maintained and documented during the clinical study.
- Ensure that maintenance and calibration of the equipment relevant for the assessment of the clinical study is appropriately performed and documented, where applicable.

